5.1 Inclusion Criteria

Participants are eligible to be included in the study only if all the following criteria apply:

Age and Weight

- 1 Participant must be aged \geq 29 weeks GA to $<$ 18 years of age at the time of signing the informed consent (see Appendix A 3 for procedures around informed consent).
- 2 Participant must weigh a minimum of 1.5 kg.

Type of Participant and Disease Characteristics

COHORT 1: Participants who do not have COVID-19 and have not knowingly been exposed to a SARS-CoV-2 positive individual (pre-exposure prophylaxis):

- 3 At increased risk of severe COVID-19 for any of the following reasons:
 - (a) Immunocompromised state
 - (b) One or more comorbid conditions that increase the risk of severe COVID-19, eg, cardiovascular disease, including heart disease since birth, malignancy, chronic kidney disease, and genetic, neurologic, or metabolic conditions.
- 4 Medically stable defined as disease not requiring significant change in therapy or hospitalization for worsening disease during the one month prior to enrollment, with no acute change in condition at the time of study enrollment as judged by the Investigator.
- 5 Documented negative SARS-CoV-2 RT-PCR test collected \leq 3 days prior to Day 1 or a negative rapid SARS-CoV-2 antigen test at screening.
- 6 Prior to enrollment, participants must not have had COVID-19 symptoms (Table 13) within 10 days of dosing.

7 Increased risk for SARS-CoV-2 infection, defined as those whose locations or circumstances put them at appreciable risk of exposure to SARS-CoV-2 and COVID-19, based on available risk assessment at time of enrollment.

COHORT 2: Participants with COVID-19 and mild to moderate symptoms (treatment):

8 At increased risk of severe COVID-19 for any of the following reasons:

- (a) Immunocompromised state
- (b) One or more comorbid conditions that increase the risk of severe COVID-19 (see list in 3[b])

9 Medically stable defined as disease not requiring significant change in therapy or hospitalization for worsening disease during the one month prior to enrollment, with no acute change in condition at the time of study enrollment as judged by the Investigator.

10 Documented positive SARS-CoV-2 RT-PCR test collected \leq 3 days prior to Day 1 or a positive rapid SARS-CoV-2 antigen test at screening.

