5.2 Exclusion Criteria

Participants are excluded from the study if any of the following criteria apply:

Medical Conditions

- 1 Cohort 1: Significant infection or other acute illness, including fever > 100 °F (> 37.8 °C) on the day prior to or day of receiving AZD7442.
- 2 History of infection with SARS-CoV-1 or MERS-CoV.
- 3 Cohorts 1 and 2: Current need for immediate medical attention in an emergency room service in the clinical opinion of the site Investigator or current need for hospitalization ([Appendix E](#)) in the following circumstances:
 - (a) Due to progressive COVID-19 as this implies severe disease (an exception is participants hospitalized with mild-moderate COVID-19 as a precautionary measure for isolation/infection prevention or for the purpose of conducting study procedures).
 - (b) For any underlying medical condition that requires hospitalization (suggestive of an unstable medical condition) with the following exceptions:
 - Neonates aged \geq 29 weeks GA to < 1 month in their birth hospitalization when discharge is expected within 7 days after receiving AZD7442.

- Children hospitalized for maintenance chemotherapy administration (induction, reinduction, relapse chemotherapy excluded). AZD7442 administration is to occur a minimum of 2 hours post chemotherapy administration (including any hydration or blood products) or post the institutional standards for observation after chemotherapy administration, whichever is longer. Only children who, in the opinion of the investigator, are at low risk for a hypersensitivity reaction to administration of chemotherapy or blood products should be considered for same day administration of AZD7442 during hospitalization for maintenance chemotherapy.

- 4 Requirement for mechanical ventilation or extracorporeal membrane oxygenation or anticipated impending need for mechanical ventilation at baseline for treatment of COVID-19 (CPAP and high flow O₂ is permitted).
- 5 Known history of allergy or reaction to any component of the study drug formulation.
- 6 Previous hypersensitivity, injection/infusion-related reaction, or severe adverse reaction following administration of a mAb for any indication.
- 7 Any co-morbidity requiring surgery within 7 days prior to study entry, or that is considered life-threatening in the opinion of the site Investigator within 30 days prior to study entry.

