Appendix A6 Dissemination of Clinical Study Data	Added text around clinical trial transparency.	To align with the newest TransCelerate protocol template
Appendix A7 Data Quality Assurance	Revised an oversight.	Correction
Appendix B4 Medication Error, Drug Abuse, and Drug Misuse	Added information on drug abuse and drug misuse.	To align with the newest TransCelerate protocol template
Various sections	Corrections, consistency alignments, and formatting updates throughout as needed	Corrections and updates for clarity

Version 3.0, 03 March 2022		
Key amendment and rationale for change:		
Section No and Name	Description of Change	Brief Rationale
1.1 Synopsis	Updated in line with the changes in the body of the protocol	See below
1.2 Schematic, 4.1 Study Design, 5.1 Inclusion Criteria	Updated in line with the changed recruitment plan for the cohorts	In response to health authority feedback
1.3 Schedule of Activities, 4.2.1 Rationale for Choice of Endpoints, Section 8.5.1 Total Blood Volume	Changed Visit 3 from Day 29 to Day 31	In response to health authority feedback. The change puts Visit 3 outside the 30-day window from Visit 1 for blood collection.
1.3 Schedule of Activities (Table 2 and Table 3)	Deleted samples for serum chemistry and hematology at	To further reduce the blood volume required for collection

Version 3.0, 03 March 2022		
	Visit 4 and coagulation tests at Visit 5	
1.3 Schedule of Activities (Table 3); Section 8.5.3.2 SARS-CoV-2 Serology	Serostatus will be collected from all participants in Cohort 1 (non-neonates)	To confirm whether Cohort 1 have previously been infected with SARS-CoV-2
1.3 Schedule of Activities, 8.6.1 Virologic Assessments	Addition of an unscheduled sample for SARS-CoV-2 RT-PCR in participants in Cohort 1 that have COVID-19 qualifying symptoms during the study	To assess SARS-CoV-2 infections in the prophylaxis cohort during the study
1.3 Schedule of Activities, 2.3.1 Risk Assessment, 4.1 Study Design, 8.3 Adverse Events and Serious Adverse Events	Clarification of the requirement to monitor participants on site for adverse reactions for one hour after IMP injection/infusion	In response to health authority feedback
2 Introduction	Added language regarding neutralizing capacity of AZD7442 against SARS-CoV-2 variants, including Omicron	To provide the latest information relative to the currently dominant Omicron variant

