**Table 1: Analysis sets**

Population/Analysis Set	Description
Screened Population Set (SPS)	All participants who signed the ICF. Unless otherwise stated, this set will be used for the presentation of disposition data.
Full Analysis Set (FAS)	All participants who received the IMP, irrespective of their protocol adherence and continued participation in the study. Participants who withdraw consent or assent to participate in the study will be included up to the date of their study termination.
Modified Full Analysis Set (mFAS)	All participants who are in the FAS, excluding participants who were assigned to Cohort 1 by rapid COVID-19 test, but have a positive confirmatory test.
Safety Analysis Set (SAF)	All participants who have received IMP.
PK Analysis Set (PKS)	All participants who received AZD7442 and from whom PK blood samples are assumed not to be affected by factors such as protocol violations, and who had at least one quantifiable serum PK observation post-dose, will be included in the PK analysis dataset.
AZD1061 ADA Evaluable Analysis Set (ADS1)	A participant is AZD1061 ADA evaluable if in the SAF and having a non-missing baseline AZD1061 ADA result and at least one non-missing post-baseline AZD1061 ADA result.
AZD8895 ADA Evaluable Analysis Set (ADS2)	A participant is AZD8895 ADA evaluable if in the SAF and having a non-missing baseline AZD8895 ADA result and at least one non-missing post-baseline AZD8895 ADA result.
AZD7442 ADA Evaluable Analysis Set (ADS3)	All participants who are AZD8895 ADA evaluable and/or AZD1061 ADA evaluable.
SARS-CoV-2 nAb Evaluable Analysis Set (SES)	All participants in the Safety Analysis Set from whom blood samples were assumed not to be affected by factors such as protocol violations, and who had at least one quantifiable serum titer observation post dose.

Generally, all listings will be prepared based on the SAF unless otherwise stated.  
Disposition data will be listed for the SPS.

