- For AZD1061, ADA negative at baseline and ADA positive at  $\geq 1$  post-baseline assessments with ADA titer  $\geq 80$
- For AZD8895, ADA negative at baseline and ADA positive at  $\geq 1$  post-baseline assessments with ADA titer  $\geq 160$

- AZD7442 is treatment-induced ADA+ if either AZD8895 and/or AZD1061 is treatment-induced ADA+

Treatment-boosted ADA+:

- For AZD1061 or AZD8895, Baseline positive ADA titer that was boosted to  $\geq 4$  - fold during study period
- AZD7442 is treatment-boosted ADA+ if either AZD8895 and/or AZD1061 is treatment-boosted ADA+

Treatment-emergent ADA+:

- For AZD1061 or AZD8895, either treatment-induced ADA+ or treatment-boosted ADA+
- AZD7442 is treatment- emergent ADA+ if either AZD8895 and/or AZD1061 is treatment- emergent ADA+

Persistently ADA+:

- For AZD1061, participants who are Treatment-emergent ADA positive, and having ADA post-baseline positive with ADA titer  $\geq 80$  at  $\geq 2$  post-baseline assessments (with  $\geq 16$  weeks between first and last positive) or positive with ADA titer  $\geq 80$  at last post-baseline assessment
- For AZD8895, participants who are Treatment-emergent ADA positive, and having ADA post-baseline positive with ADA titer  $\geq 160$  at  $\geq 2$  post-baseline assessments (with  $\geq 16$  weeks between first and last positive) or positive with ADA titer  $\geq 160$  at last post-baseline assessment
- AZD7442 is persistently ADA+ if either AZD8895 and/or AZD1061 is persistently ADA+

Transiently ADA+

- For AZD1061, participants who are Treatment-emergent ADA positive, and having at least one post-baseline ADA positive assessment with titer  $\geq 80$  and not fulfilling the conditions of persistently positive
- For AZD8895, participants who are Treatment-emergent ADA positive, and having at least one post-baseline ADA positive assessment with titer  $\geq 160$  and not fulfilling the conditions of persistently positive
- For AZD7442, treatment-emergent ADA positive and not fulfilling the conditions of persistently positive.

The number and percentage of AZD7442, AZD8895 and AZD1061 ADA-evaluable positive/negative participants in each cohort will be determined. The number of ADA-

evaluable participants in the cohort will be used as the denominator for percentage calculation.

To evaluate the ADA responses to AZD7442, AZD8895 and AZD1061 in serum the following analyses will be presented:

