#### **4.2.4 Secondary Endpoint – Cohort 1 (Prophylaxis)**

To evaluate the incidence of SARS-CoV-2 infections with or without COVID-19 symptoms after a single IM or IV dose of AZD7442 in pediatric participants, when a participant develops at least one of the COVID-19 qualifying symptoms (see Section [Disease Characteristics4.1.6](#)), an unscheduled visit is performed and a SARS-CoV-2 RT-PCR test is performed to confirm the participant is positive. Additionally, to identify

symptom-free SARS-CoV-2 infections, serology testing is performed at each visit. Any positive SARS-CoV-2 test result indicating infection as well as any symptoms will be reported as an AE.

Incidence will be determined by AE and summarized via frequency and proportion of participants in the SAF by weight categories and route of administration. SARS-CoV-2 serology test results will be summarized by count and number of observations for each timepoint and cohort.

This summary will be repeated for participants in the mFAS.

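### The SAP counts Cohort 1 infection by AE with no serostatus or seroconversion rule, lists 12 of the 19 qualifying symptoms, and dates progression by AE only

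*SAP*

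**What the plan says.** **Cohort 1 infection.** SAP 4.2.4 states: "Incidence will be determined by AE and summarized via frequency and proportion of participants in the SAF by weight categories and route of administration". On what feeds that count it says: "Any positive SARS-CoV-2 test result indicating infection as well as any symptoms will be reported as an AE". It adds that, in order to pick up "symptom-free SARS-CoV-2 infections, serology testing is performed at each visit". Serology results are then tabulated by timepoint and cohort. The incidence summary is repeated in the mFAS, which is the FAS "excluding participants who were assigned to Cohort 1 by rapid COVID-19 test, but have a positive confirmatory test".

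On entry, protocol 5.1 asks for a documented negative RT-PCR collected no more than 3 "days prior to Day 1 or a negative rapid SARS-CoV-2 antigen test at screening". Exclusion 2 in protocol 5.2 reads "History of infection with SARS-CoV-1 or MERS-CoV"; past SARS-CoV-2 infection is not listed. Protocol 8.5.3.2 says that baseline serostatus and time to seroconversion will be determined with a nucleocapsid (anti-N) assay. Protocol Appendix H gives the purpose of Cohort 1 serology as "To confirm whether Cohort 1 have previously been infected with SARS-CoV-2". Protocol Table 1 schedules screening serology for everyone except neonates. Table 3 schedules it afterwards for Cohort 1 non-neonates at Visits 3 to 6 and at early discontinuation.

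**Symptoms.** SAP 4.2.4 refers to SAP 4.1.6 for the qualifying symptoms. That list stops at sore throat. Protocol Table 13 goes on.

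**Progression.** SAP 4.2.5.2 counts worsening or new symptoms reported through AEs and weekly contact, or COVID-19 hospitalization or death, up to Day 29. It calculates time to progression from the AE date. Protocol 8.1.1 makes a Table 13 symptom an AE in Cohorts 2 and 3 only if it is serious, leads to discontinuation, or is judged unrelated to COVID-19.

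**The concern.** Infection incidence is the protocol's secondary endpoint for Cohort 1, and it covers infection with and without symptoms after dosing. For the symptom-free part, serology is the only scheduled means of detection after Day 1. Anti-N positivity marks past as well as new infection, so the result has meaning only against the child's own screening value. The SAP has that value for non-neonates but does not use it in the incidence rule. It leaves the decision to whichever results sites report as AEs, and the documents give sites differing instructions on that.

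The other two gaps are narrower. The Cohort 1 symptom table would omit the nasal, gastrointestinal and feeding symptoms that the protocol treats as qualifying. The time-to-progression summary would describe fewer events than the progression proportion beside it.

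**Working it through.** The plan states no figure to reproduce here: no hypotheses are tested and no incidence is assumed.

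**1. Which Cohort 1 positives become AEs**

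- SAP 4.2.4: any positive test indicating infection, with no baseline condition.
- Protocol 8.1.1: qualifying symptoms, positive results and/or a COVID-19 diagnosis, with no baseline condition.
- Protocol 4.1: a positive result after baseline in a child who was negative at baseline and developed symptoms.

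Under the first two, a child anti-N positive at screening and again at Day 31 may be reported, depending on how the site reads the words on indicating infection. Under the third, a child who seroconverts without symptoms need not be reported. The mFAS settles neither case, because it removes children by confirmatory test and not by serostatus. For ADA the SAP does write the kind of rule needed: "ADA negative at baseline and ADA positive at" one or more later assessments, with a titer threshold.

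**2. Illustration of both directions (assumed values; the documents give none)**

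Let s be the share seropositive at baseline and i the new-infection rate among seronegatives. Suppose every baseline-positive child stays positive and is reported. Then the apparent incidence is s + (1 − s) × i. With i = 10%:

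- s = 10%: 0.10 + 0.90 × 0.10 = 19%
- s = 30%: 0.30 + 0.70 × 0.10 = 37%
- s = 50%: 0.50 + 0.50 × 0.10 = 55%

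A rule restricted to baseline seronegatives gives 10% each time. In the other direction, suppose only symptomatic cases become AEs and a share a of infections is symptom-free. A true 10% is then counted as 10% × (1 − a): 8%, 6% or 4% for a = 20%, 40% or 60%.

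**3. Influence of one child**

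- SAP section 2 gives 46 in the FAS. If all were in Cohort 1, one child is 1/46 = 2.2 points.
- Protocol Table 5 plans at least 19 IM + 12 IV = 31 in Cohort 1: 1/31 = 3.2 points.
- Four weight categories hold at most 46/4 = 11.5 on average: 1/11.5 = 8.7 points.
- At least 2 of the planned 31 are neonates (6.5%), who have no serology but stay in the denominator.

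**4. Serology timing**

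Protocol Table 3 has seven visits (1, 2, 2A, 3, 4, 5, 6). Serology falls at four of them (3 to 6), plus early discontinuation, so the SAP's statement that it is done at every visit is not correct.

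**5. Symptom lists**

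Table 13 has 3 symptoms with no minimum duration and 16 needing at least 2 days, 19 in all. SAP 4.1.6.1 has 3 + 9 = 12, all of them in Table 13. The missing 7 (7/19 = 37%) are congestion, runny nose, nausea, vomiting, diarrhea, abdominal pain, and poor appetite or feeding problems. SAP section 2 declares no such change.

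**6. Progression**

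Take a Cohort 2 child with a new, non-serious, COVID-19-related symptom reported at a weekly contact. SAP 4.2.5.2 counts this as progression. Protocol 8.1.1 keeps it out of the AE data. The formula (AE date − Day 1 + 1) then has no date to use. Severe COVID-19, hospitalization and death are recorded as SAEs and do have dates.

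**The case against.** The strongest reply is that incidence is counted by AE and not by raw serology. Protocol Appendix B defines an AE as something that develops, and section 8.3.1 collects AEs from dosing onward. A child who was positive at screening and is unchanged at Day 31 has developed nothing, and the SAP limits AEs to results that indicate infection. This stands in part. A reader might infer that the endpoint is inflated, but the documents do not support that: an overcount needs a site to report an unchanged positive, and protocol 4.1 pushes the other way. What remains is that the result depends on site practice under differing instructions.

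A second reply is that replacing the AE route with laboratory data alone could lose real cases. This stands. Protocol 8.6.1 says that unscheduled RT-PCR may be performed, so a neonate or a baseline-seropositive child with a diagnosis after dosing but no study RT-PCR would be missed. The seroconversion rule should add to the AE route.

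Third, little is lost through the short symptom list. Sites work from protocol Table 13, and Cohort 1 qualifying symptoms are recorded as AEs. A reader might infer that infections go untested or that symptoms vanish from the data; neither follows.

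Fourth, time to progression is not a protocol endpoint, Cohort 3 is empty, and the eCRF may hold a progression date. All true. The SAP formula still does not use that date.

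Finally, the per-child figures are 1/n and would hold for any summary in a study of this size. They show sensitivity and do not estimate bias.

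**Conclusion.** The point holds as three wording gaps in descriptive summaries. The Cohort 1 rule is the substantive one: a protocol secondary endpoint lacks a serostatus and seroconversion definition that the protocol anticipates and the scheduled data allow. It can err upward or downward. The net direction and size are unknown, because baseline seroprevalence, the symptom-free share and site reporting practice are not given. The percentages in step 2 of the working rest wholly on assumed values.

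The symptom list affects the Cohort 1 symptom summary and possibly the split into infections with and without symptoms. It does not affect testing at sites or the AE listings. The dating formula affects the time summary in Cohort 2 only. It would be wrong to conclude that the protocol endpoint, the proportion progressing through Day 29, is affected. No error rate or sample size changes.

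**What to change.** **SAP 4.2.4.** Count a Cohort 1 infection as any of:

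- (a) a positive RT-PCR or other positive viral test after dosing;
- (b) a COVID-19 diagnosis AE with onset after dosing;
- (c) anti-N negative at screening and positive at a later sample.

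State that a positive anti-N result in a child already positive at screening does not count by itself. Report (c) among children anti-N negative at screening with at least one later serology result, which leaves out neonates. Report (a) and (b) for all of Cohort 1. Show the numbers of baseline-seropositive and untested children alongside, and keep the mFAS repeat. Correct the serology timing to Visits 3 to 6 and early discontinuation, Cohort 1 non-neonates.

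**Protocol 4.1 and 8.1.1.** Reconcile which positive Cohort 1 results are AEs.

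**SAP 4.1.6.1.** Use the full protocol Table 13 and state that it defines the split by symptoms.

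**SAP 4.2.5.2.** Date progression by the earliest of the eCRF or weekly-contact symptom date, COVID-19-related AE, hospitalization or death.

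**Cost.** SAP text, programming and alignment of two protocol sections, with no new sample or visit. The serologic denominator becomes smaller. Weekly-contact dates may be accurate only to about 7 of the 28 days to Day 29 (25%) unless symptom onset is recorded.

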#### **4.2.5 Secondary Endpoint – Cohort 2 and Cohort 3 (Treatment)**

##### **4.2.5.1 Viral load**

To quantify SARS-CoV-2 viral loads after a single IM or IV dose of AZD7442 in pediatric participants, the log10-transformed observed results and changes from baseline to Day 8 in log10-transformed viral load as measured by qRT-PCR will be summarized for the SAF by weight categories, dose, and route of administration.

##### **4.2.5.2 Progression of COVID-19**

To evaluate the proportion of participants with progression of COVID-19 after a single IM or IV dose of AZD7442 in pediatric participants, the count and percentage of participants in the SAF with worsening of COVID-19 will be determined by occurrence of an increase in symptom severity (reported through AEs and the weekly contact) one or more new symptoms (reported through AEs and the weekly contact) or hospitalization or death related to COVID-19 up to day 29 (inclusive). The summary will be tabulated by cohort.

The time to (first) progression [date of AE – date of Day 1 +1] will also be listed and summarized via n, median, 1st and 3rd quartile, minimum, and maximum by weight categories, dose, and route of administration for the SAF.

